Exclusion criteria	
1. On lipid-lowering medication solely for secondary prevention of ASCVD events with evidence of pre-medication non-HDL which was already below 100mg/dL2. On anti-hypertensive medications solely for a non-hypertension indication (e.g. systolic heart failure),3. Severely hearing or speech impaired, or other disability that would limit participation in the intervention components, and4. In a nursing home and/or receiving in-patient psychiatric care.5. Terminal illness with life expectancy < 4 months6. No reliable access to a telephone7. Pregnant, breast-feeding, or planning a pregnancy during the study period8. Planning to move out of the area in the next 12 months9. Non-English speaking
Endpoints	
Primary Endpoints
 
• 12-month change in systolic blood pressure 
Secondary Endpoints
 
• 12-month change in non-HDL cholesterol• Change in the extended cascade categories [(1) % appropriately diagnosed, (2) % appropriately managed, and (3) % at treatment goal]

Key Roles

Co-Principal Investigator	[name] University of Washington [contact]
Site Principal Investigator	[name] Professor of Medicine Case Western Reserve University University Hospitals Cleveland Medical Center [name] [name] [contact]
Co-Principal Investigator	[name], PhD University of Washington [contact]
Co-Principal Investigator	[name] Professor of Medicine Duke Department of Population Health Sciences [name] [contact] [contact]
Co-Investigators	[name] MetroHealth Medical Center Cleveland, OH
	[name] New York University New York, NY
	[name] Duke University School of Medicine Durham, NC
	[name] Duke University School of Medicine Durham, NC
Lead Statistician	[name] Duke University School of Medicine Durham, NC

1. Background

The HIV/AIDS treatment cascade model was developed to assess how people living with HIV infection (PLHIV) access care and treatment. The model includes sequential steps in care including—(1) diagnosis, (2) prescription of appropriate antiretroviral therapy (ART), and (3) suppression of detectable HIV virus in the blood. These metrics are familiar to HIV-providers and integral to continuous quality improvement initiatives at HIV specialty clinics across the United States, where most PLHIV receive care¹.

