We envision extending the HIV treatment cascade for two key CVD risk factors—blood pressure and cholesterol—to improve uptake of guideline-based ASCVD prevention therapies. **Step 1**, PLHIV should have their blood pressure and cholesterol screened, and abnormal values should be appropriately diagnosed as

hypertension and hypercholesterolemia in the medical record; **Step 2**, those with hypertension or hypercholesterolemia should be prescribed appropriate guideline-based therapies; and **Step 3**, all should achieve guideline-based treatment goals. Developing the HIV treatment cascade for prevention of non-AIDS comorbidities is a logical downstream extension of the treatment cascade paradigm, just as the HIV prevention cascade is extending the treatment cascade further upstream¹⁹ (Figure 1).

Blood pressure and cholesterol targets matter. To our knowledge, no HIV-specific blood pressure guidelines exist; however, international guidelines generally agree that treating to a target systolic blood pressure of 140mmHg for most patients is appropriate, while acknowledging that certain groups may merit more aggressive targets (e.g. <130 systolic for diabetes and chronic kidney disease)^{20,21}. The most recent AHA/ACC guidelines go further to recommend both pharmacologic and non-pharmacologic strategies to achieve a treatment target of <130mmHg for most patients²²; although these recent guidelines have yet to achieve widespread

[figure not shown]

Figure 1: The extended HIV treatment and prevention cascade

Table 1: NLA treatment goals for PLHIV.

Risk Category	Criteria	NLA goal Non-HDL-C LDL-C
Low	N/A*	N/A*
Moderate	2 major risk factors (i.e. HIV + high BP only)	<130 mg/dl <100 mg/dl
High	≥ 3 major risk factors	<130 mg/dl <100 mg/dl
Very High	Known ASCVD OR Diabetes +≥ 2 major risk factors *	<100 mg/dl <70 mg/dl

Major risk factors include: HIV, Age >45 men or >55 women, family history of early CAD, smoking, hypertension, low HDL-C.

* By design, all participants in our study will be > low risk and those with diabetes will be very high risk.

implementation. To achieve these targets, many will require more than one drug and a lifetime of titrating medication. Improving self-management is thus a critical component to successful treatment of blood pressure over time.²³

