- **Part 2: Delphi Process:** This part of the study will further refine the list of variables generated during the group concept mapping phase to create a final composite measure of dose that incorporates different weights given to variables based on what stakeholders believe to be the most important aspects of the intervention. There will be 3 rounds of questionnaires to complete online and the total time required will be ~30-45 minutes.

The final composite measure of dose that results from this process will be used in analyses as a potential mediator of EXTRA-CVD outcomes, including both primary and secondary clinical outcomes (BP & cholesterol) but also implementation outcomes and other outcomes of interest (i.e. time to disengagement for those who are lost to follow-up).

Aim 2 Procedures:

We will conduct a randomized controlled trial of the EXTRA-CVD intervention vs. education control among PLHIV on suppressive ART who have both hypertension and hypercholesterolemia. Control participants will receive general prevention education. The intervention—contextually adapted during sub-aim 1.1—will consist of prevention education plus 4 additional evidence-based components: (1) **nurse-led care coordination**, (2) **EMR alerts and decision support**, (3) **home BP monitoring**, and (4) **nurse-managed medication protocols and adherence support**. The primary outcome is change in systolic BP and the secondary outcome will be change in non-HDL cholesterol. Separately for hypertension and hypercholesterolemia, we will then examine changes in the three extended treatment cascade categories [(1) % appropriately diagnosed, (2) % appropriately managed, and (3) % at treatment goal]. We chose BP as the primary outcome because the EXTRA-CVD intervention components

were designed primarily to address BP management, with cholesterol management being an important but secondary consideration. For the purposes of determining cascade level #1, we will use the following table to search for diagnosis of high cholesterol or blood pressure in the medical record.

Table: Diagnosis terms for high cholesterol and high blood pressure for the purposes of determining cascade category from chart review.

High Cholesterol	High Blood Pressure
Hyperlipidemia	Hypertension
Dyslipidemia	Essential Hypertension
Hypertriglyceridemia	Secondary Hypertension
Hypercholesterolemia	Hypertensive end-organ disease
Elevated LDL	High blood pressure
Elevated Triglycerides	
Elevated Cholesterol	

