3. Home BP monitoring. Our justification for using home BP monitoring in the EXTRA-CVD intervention is that home BP measurements are reproducible with standard deviations of less than 3.1 mmHg for both systolic and diastolic measurements⁸⁴. In addition, home BP monitors are accurate and comparable to ambulatory BP monitors⁸⁵, a ‘gold standard’ of BP measurements. Home measurements have greater predictive power for mortality as compared to office-based measurements.⁸⁶ All intervention participants will receive a home BP monitor and will be trained according to a developed protocol¹⁴ and documentation of proper usage will be recorded. Participants will use the BP monitors every day. Prior to each telephone or in-person follow-up visit, we will request BP values for the past two weeks using a standardized data collection form. Participants with poor BP control will receive nurse calls every 2 weeks, with management changes made as described in component #2 above. All intervention participants will be able to keep the BP monitor after completion of the study. Control participants will receive a BP monitor and instructions about its use after completion of the final 12-month trial visit.

Component 3—Relevant process evaluation data for aim 3: (1) Frequency of home BP checks (average checks/week and proportion of weeks with ≥ 2 checks); (2) Number and nature of medication changes in response to home BP data; (3) Barriers to home BP use; (4) Knowledge of proper home BP use.

4. EMR support tools. Evidence-based EMR tools that do not result in provider fatigue or information overload effectively improve patient outcomes^{87,88}. Our three sites use two of the most widely available EMR systems (Epic at MetroHealth/Duke and Allscripts at UH). At the UH Special Immunology Unit, there is also a parallel electronic database that may be used for clinical purposes and is amenable to programmable tools. Beginning in year 1, we will work locally with EMR (IT) support to develop these tools to assist the prevention nurse during the intervention phase:

- An extended treatment cascade graphic for the prevention-nurse specialist which will appear on his/her “dashboard” or as a recurring pdf report. During the intervention phase, the nurse will have regular access to this graphic and will receive names of specific patients who have fallen out of each cascade category.
- Tool to chart home blood pressures in EMR.

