For the tertiary outcome of cascade category, we will calculate an ordinal four-level variable at baseline, 4, 8, and 12 months. We will use a proportional odds model fit via generalized estimating equations to examine differences over time between study arms. The proportional odds assumption will be assessed using score tests, and the model will be relaxed to partial proportional odds if necessary. Robust sandwich standard errors will be used to account for potential overdispersion and correlation among the repeated observations over time. Similarly to the primary analysis, the model will adjust for clinic site and include the same general mean model specification. The primary hypothesis will be tested via SAS PROC GENMOD to assess whether the estimated proportions in each level at 12 months differ between arms. All analyses will be conducted following an intention to treat (ITT) principle.

Missing Data:

We will assess mechanisms for missing data in this study. LMM, implicitly accommodates missingness when the response is Missing At Random (MAR); that is, when missingness is due either to treatment, to prior outcome, or to other baseline covariates included in the LMM. We will address missing data by imputing missing values using multiple imputation procedures as described by Schafer. Once missing values have been imputed, each multiply-imputed data set can be analyzed using the LMM. Final parameter estimates and their standard errors will be calculated using Rubin's formula. We will analyze our data and report final study results with and without employing the multiple imputation strategy (compared to complete case analysis) and carefully examine and describe any discrepancies found.

Power:

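### The cascade outcome is listed as three percentages per condition, but the only planned analysis is of an undefined four-level score that cannot return them

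*Combined protocol and SAP*

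**What the plan says.** The synopsis of the combined protocol and SAP lists under secondary endpoints: "Change in the extended cascade categories [(1) % appropriately diagnosed, (2) % appropriately managed, and (3) % at treatment goal". Aim 2 Procedures repeats this by condition: "Separately for hypertension and hypercholesterolemia, we will then examine changes in the three extended treatment cascade categories".

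The steps draw on different sources:

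- **Diagnosed** depends on finding a listed term in the chart (Aim 2 Procedures, table of diagnosis terms).
- **Managed** is described in Significance: "those with hypertension or hypercholesterolemia should be prescribed appropriate guideline-based therapies". There is no operational definition.
- **At goal** is stated there without restriction to treated people: "all should achieve guideline-based treatment goals".

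Statistical Considerations, which calls the outcome tertiary, analyses it differently: "we will calculate an ordinal four-level variable at baseline, 4, 8, and 12 months", then "We will use a proportional odds model fit via generalized estimating equations", testing the level proportions by arm at 12 months. It does not say what the four levels are, how a participant who meets a later step but not an earlier one is scored, or how the three percentages will be compared.

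**The concern.** A four-level score carries the same information as three percentages only if the steps are nested, so that everyone at goal is managed and everyone managed is diagnosed. The Aim 2 entry criteria do not produce that. Hypertension qualifies on repeated systolic readings above 130 or on medication. Hyperlipidemia qualifies on a non-HDL value above 130 or on medication. Neither requires a chart diagnosis. A medicated participant without a listed term is eligible. So is an untreated participant with elevated values, who may later fall below the goal.

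At stake is whether the trial can report its own listed outcome. With the rule open, it could also be chosen after the data are seen, and the same choice carries into the pre-specified subgroup analyses, which cover this outcome too. On one natural rule, the share in the top level can rise because more people are diagnosed or prescribed for, with no change in any measured value.

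**Working it through.** **1. Patterns and candidate scores.** Write each participant as (diagnosed, managed, at goal). The plan states no rule, so three plausible ones are shown.

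| Pattern | Sequential | Highest step | Count |
|---|---|---|---|
| 000 | 0 | 0 | 0 |
| 100 | 1 | 1 | 1 |
| 110 | 2 | 2 | 2 |
| 111 | 3 | 3 | 3 |
| 001 | 0 | 3 | 1 |
| 010 | 0 | 2 | 1 |
| 011 | 0 | 3 | 2 |
| 101 | 1 | 3 | 2 |

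The rules agree on the four nested patterns and differ on the rest. Under sequential scoring the at-goal patterns 001, 011 and 101 fall below 110 (diagnosed, managed, uncontrolled). Under count scoring only 001 does. Under highest-step scoring none does.

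**2. Can any four-level score return the three percentages?** If two patterns share a level, moving a participant from one to the other leaves the level proportions unchanged but alters at least one percentage. Each level can therefore hold only one pattern, and four levels hold four. An exhaustive search agrees:

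- All 8 patterns (4^8 = 65,536 maps): 0 work.
- The 6 patterns left if at goal is taken to imply managed (4^6 = 4,096 maps): 0 work.
- The 4 nested patterns: 24 work, the 4! one-to-one maps.

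**3. What each reading reports.** Rates are assumed, because the documents give none: 85% diagnosed, 90% managed, 48% at goal, independent. This shows the mechanism only.

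- Sequential, level 1 and above: 85%. Level 2 and above: 0.85 × 0.90 = 76.5%. Level 3: 0.765 × 0.48 = 36.7%. Only the diagnosed share is right.
- Highest step, level 1 and above: 1 − 0.15 × 0.10 × 0.52 = 99.2%. Level 2 and above: 1 − 0.10 × 0.52 = 94.8%. Level 3: 48%. Only the at-goal share is right.

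**4. How many might be at goal but untreated?** The plan states no cascade rate or power, so there is no figure to reproduce. Inputs from the Power section: SBP mean 145, SD 17, correlation 0.4; non-HDL mean 132, SD 41, correlation 0.7. The threshold is taken as 130 for both. Untreated people enter only above 130, so goal status must be conditioned on entry.

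- SBP: a = (130 − 145)/17 = −0.882. One, two and three correlated values all below 130 have probability 0.1888, 0.0698 and 0.0345. Two entry readings above 130: 1 − 2(0.1888) + 0.0698 = 0.692. Two above and a later one below: 0.1888 − 2(0.0698) + 0.0345 = 0.084. Ratio: 0.084/0.692 = 12%.
- Non-HDL: b = (130 − 132)/41 = −0.049. One value below 130: 0.4805. Two below: 0.3541. A later value below, given entry above: (0.4805 − 0.3541)/(1 − 0.4805) = 24%.

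Multiply by the untreated share (assumed 20–30%):

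- BP: 0.121 × 0.20 to 0.30 = 2.4–3.6%, or 7–11 of 300.
- Non-HDL: 0.243 × 0.20 to 0.30 = 4.9–7.3%, or 15–22 of 300.

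With 10–40% untreated the ranges are 1.2–4.8% and 2.4–9.7%.

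**The case against.** A reader might infer that the plan ranks controlled participants below uncontrolled ones. The documents do not support that as a firm finding. The inversion needs a sequential or count rule, and none is stated. Significance numbers the cascade steps, which makes a sequential rule natural. But the explicit mention of sequence describes the HIV treatment cascade, and the reference to "names of specific patients who have fallen out of each cascade category" describes a nurse's report, not this variable.

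A reader might also equate managed with being on a drug. The plan does not, and Significance notes that guidelines recommend non-drug strategies too. A diagnosed, unmedicated participant at goal might therefore count as managed, and a medicated, uncontrolled one might not. This objection stands. It does not restore nesting: if everyone at goal counts as managed, a missing chart term still leaves six patterns.

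Third, one might apply the unconditional shares below 130 (19% SBP, 48% non-HDL) to untreated people and get roughly 4–6% and 10–14%. That ignores entry selection and overstates the group.

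Finally, a reader might fear a spurious cascade benefit. Assume 90% diagnosed, prescribing raised from 70% to 85% and no change in values. The sequential top level then rises by 0.90 × 0.15 × 0.189 = 2.6 points (SBP) and 0.90 × 0.15 × 0.481 = 6.5 points (non-HDL). If the newly treated have the entry-selected shares, the rises are 0.90 × 0.15 × 0.121 = 1.6 and 0.90 × 0.15 × 0.243 = 3.3 points. With 150 × 0.85 = 127.5 per arm at 12 months, the standard error of the difference is about 4.2 points for SBP, √[(0.119 × 0.881 + 0.145 × 0.855)/127.5], and 5.9 for non-HDL, √[(0.303 × 0.697 + 0.368 × 0.632)/127.5]. SBP and non-HDL are also analysed directly, from blinded measurements, so a cascade gain without a risk-factor change would be visible. A misleading result is possible but not shown to be likely.

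**Conclusion.** The mismatch holds and does not depend on assumed rates: the listed outcome is three percentages per condition, and the only method given is for a score whose levels are undefined. Because the steps are not nested, defining the levels would not by itself recover the percentages. They need their own analysis.

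The consequences depend on the rule. A sequential rule turns the at-goal level into a joint condition and can misrank some controlled participants. A highest-step rule avoids that and overstates the managed share. The size cannot be computed from the documents. The illustration of 2–4% (BP) and 5–7% (non-HDL) at goal but untreated assumes:

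- 20–30% untreated, and still untreated at the later visit;
- chart and study values sharing the Power section's distribution and correlations, with no drift;
- a goal of 130 throughout, although the cholesterol algorithm sets a lower non-HDL goal for higher-risk participants.

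Whether those people are misranked also depends on how appropriate management is defined. The point is worth correcting, but it concerns an outcome that Statistical Considerations calls tertiary.

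**What to change.** In Statistical Considerations:

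- Define the three yes/no indicators, including what counts as appropriately managed and which of the protocol's goals applies to each participant.
- Add a binary logistic GEE for each of the three steps, for hypertension and for hypercholesterolemia separately, with the same site adjustment and 12-month arm contrast.
- Score the at-goal indicator in every randomised participant from the study-measured SBP or non-HDL, whatever the chart term or prescription.
- The ordinal model may stay as a summary, one score per condition, if its level rule is written in advance for all eight patterns.

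The cost is SAP wording and 3 × 2 = 6 models on data already planned. The downside is a few more tests on a tertiary outcome. Dropping the ordinal model, or naming one step as the lead outcome, is not needed to close the gap.

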The primary outcome will be systolic BP at 12 months and secondary outcome will be non-HDL cholesterol at 12 months, both measured at 4 time-points (0, 4, 8, and 12 months). All BPs used for outcomes will be obtained by a blinded research assistant and cholesterol levels will be measured by lab personnel who are also blinded to treatment group. Because the outcomes are continuous, linear mixed-effects models⁸⁹ (LMM) will be used to examine the differences over time between the study arms. LMM will allow us to implicitly account for the correlation between a patient's repeated measurements over time. The general mean structure of the LMM we will use to examine the hypotheses is, $Y_{ij} = \beta_0 + \beta_1 * I(month = 4) + \beta_2 * I(month = 8) + \beta_3 * I(month = 12) + \beta_5 * arm * I(month = 4) + \beta_6 * arm * I(month = 8) + \beta_7 * arm * I(month12)$, where Y_{ij} represents the outcome of interest (i.e., SBP or non-HDL) for patient i at time j. In this model, we fit a common intercept and arm is the intervention group indicator. Similarly, time is classified, where for example, $I(month = 12)$ is a dummy variable equal to 1 for the 12 month time point. Random intercepts will be included for

each individual to account for correlation among repeated measurements over time. The primary analytic model will adjust for clinic site. The mixed effects model parameters will be estimated and tested using SAS PROC MIXED (SAS Institute, Cary, NC), and the hypothesis of between-arm differences over time will be tested using estimate statements within PROC MIXED. In particular, β_7 , the estimated difference in outcome between arms at 12 months, will be the primary effectiveness outcome assessed.

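### Cascade outcome: the ordinal GEE borrows the mixed model's common intercept but not its correlation model, so as written the 12-month contrast is essentially unadjusted for baseline level and loses precision

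*Combined protocol and SAP*

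**What the plan says.** All of this is in the combined protocol and SAP, under Statistical Considerations.

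- **Outcome.** The cascade category is an "ordinal four-level variable at baseline, 4, 8, and 12 months", so baseline enters as a response row. The synopsis lists it among the secondary endpoints; Statistical Considerations calls it tertiary. Aim 2 Procedures says hypertension and hypercholesterolemia are examined separately.
- **Model.** It is a "proportional odds model fit via generalized estimating equations". On covariates and mean structure, "the model will adjust for clinic site and include the same general mean model specification".
- **Borrowed mean structure.** This has month indicators and arm-by-month terms but no arm main effect: "In this model, we fit a common intercept and arm is the intervention group indicator".
- **Correlation.** In the mixed model for SBP and non-HDL, "Random intercepts will be included for" each person. In the cascade model, "Robust sandwich standard errors will be used to account for potential overdispersion and correlation among the repeated observations over time". No working association is named.
- **Test.** "The primary hypothesis will be tested via SAS PROC GENMOD", and the target is whether the proportions in each level at 12 months differ between arms.

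**The concern.** Dropping the arm main effect is a standard way to adjust for baseline in a mixed model for repeated measures. It works through the covariance: because baseline and month 12 are modelled as correlated, a chance baseline difference between arms is partly subtracted from the month-12 contrast. The random intercept that does this belongs to the correlation model, so taking over a mean model does not bring it along. Sandwich standard errors do not replace it. They correct the variance of an estimate but do not change the estimate.

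If the GEE uses working independence, baseline rows inform only the shared cutpoints and the common baseline. The month-12 arm term is then driven by month-12 data. Randomization is stratified by site alone, and eligibility admits people already on treatment, so baseline cascade level will vary and its balance between arms is left to chance. At stake are the precision of this outcome and its sensitivity to that chance imbalance.

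**Working it through.** **Step 1. Reproduce the plan's own figures.** The documents give no power, effect size or category rates for the cascade outcome. The nearest stated figures use the same mean structure, for SBP and non-HDL. Inputs from the Power section: N = 300, 1:1; two-sided alpha 0.05; 5%, 10% and 15% missing at months 4, 8 and 12; SBP SD 17 and correlation 0.4; non-HDL SD 41 and correlation 0.7.

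The generalised least squares variance of the month-12 arm term was computed for the common-intercept model with compound symmetry and monotone dropout. Power is 87.1% for 6 mmHg (stated: above 80%) and 98.5% for 15 mg/dL (stated: above 90%). In the sample-size table, 14 of 18 entries agree within 3% or 2 patients. The largest gaps (for example 234 stated against 247 computed, for 6 mmHg at 80%) are of the order expected from 1,000 simulated datasets, where the Monte Carlo SE is about 1.3 points. The mean structure has been read correctly.

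**Step 2. Same mean model, working independence.** Each arm has 150 × 0.85 = 127.5 people at month 12.

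- SBP: SE = 17 × √(2/127.5) = 2.13. Power = Φ(6/2.13 − 1.96) = 80.5%.
- Non-HDL: SE = 41 × √(2/127.5) = 5.13. Power = Φ(15/5.13 − 1.96) = 83.2%.

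These SEs are those of the raw comparison of month-12 means, and the independence model returns exactly these powers. Its variance, relative to the model with correlation, is 1.20 at correlation 0.4, 1.59 at 0.6 and 2.00 at 0.7. The two-visit approximation 1/(1 − ρ²) gives 1.19 at 0.4 and 1.96 at 0.7, in line with this. So the common intercept adjusts for baseline only through modelled correlation.

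**Step 3. Ordinal outcome.** A four-level proportional-odds outcome was simulated with N = 300 and 15% missing at month 12. *Assumed:* 12-month odds ratio 1.8; baseline splits 10/15/35/40% and 25/25/25/25%; latent within-person correlation 0.4 to 0.7. There were 400 to 600 datasets per setting (Monte Carlo SE about 2 points), with sandwich errors throughout. The exchangeable version held the working correlation at 0.75 × the latent value. The covariate version was a 12-month proportional odds model with baseline level as covariate. Power, as the range over the two splits:

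| Latent correlation | Common intercept, independence | Common intercept, exchangeable | Baseline level as covariate |
|---|---|---|---|
| 0.4 | 69–71% | 73–78% | 73–78% |
| 0.6 | 73–76% | 83–88% | 84–86% |
| 0.7 | 69–74% | 88–90% | 89–90% |

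The correlation of the month-12 log odds ratio with chance baseline imbalance is 0.29 to 0.62 under independence, 0.03 to 0.17 with exchangeable correlation, and −0.07 to 0.10 with the covariate. Under the null, independence gives a mean estimate of about 0 and rejects in 4.3 to 7.2% of datasets (SE about 1 point).

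**Step 4. Second simulation.** With an assumed split of 10/20/35/35%, a latent shift of 0.33 SD and 260 runs (SE about 3 points), power was 65% under independence against 71% with the covariate at correlation 0.4, and 66% against 78% at 0.6. Over 24 datasets, the common-intercept independence estimate correlated 0.98 to 0.99 with a proportional-odds fit to month 12 alone (mean SE 0.219 against 0.214).

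**The case against.** The plan does not say working independence; it says nothing about the working association. A reader might infer that a common intercept can never adjust for baseline in a GEE. That is not so: with an exchangeable working correlation the same mean model recovers the lost power and removes most of the dependence on imbalance (Step 3). A reader might try to settle the matter from the named SAS procedure, but the documents do not say which association structures it offers for ordinal data, and the point does not need it.

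A reader might also infer that baseline cascade data go unused. They do not: baseline is a response row and informs the cutpoints and the common baseline. What is missing is a baseline covariate, or a stated association that would do its work. Nor is the result biased. The null results show near-nominal error, and the standard error already carries the chance imbalance.

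The remaining objections concern weight. Statistical Considerations treats the outcome as tertiary and claims no power for it. Every input specific to the cascade is assumed, and at correlation 0.4 the loss is modest. An unadjusted marginal GEE is a defensible, if less efficient, choice, and it keeps the marginal target that the plan describes, whereas a covariate makes the odds ratio conditional.

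All of this stands. It limits the claim to precision and requires the fix to return to 12-month proportions. It does not remove the gap: the only treatment of correlation in the cascade section is the sandwich variance, and that gives no baseline adjustment.

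**Conclusion.** The point holds as one about efficiency and incomplete specification. Read as written, the cascade model gives essentially an unadjusted 12-month comparison. The estimated cost is about 4 to 20 power points for latent correlations of 0.4 to 0.7. That range rests on assumed category splits, an assumed odds ratio of 1.8, and working independence, which the wording suggests but does not state. The values 0.4 and 0.7 are the plan's correlations for continuous SBP and non-HDL, not for cascade level.

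The documents do not support a stronger conclusion of bias, inflated type I error or an invalid test. The SBP and non-HDL mixed models are not affected, because their random intercepts supply the link to baseline. The virtual arm (Aim 4) is outside the point, since it collects no study BP or cholesterol outcome measurements. This is a cheap improvement.

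**What to change.** Separately for BP and cholesterol, fit the ordinal GEE to months 4, 8 and 12. Include baseline cascade level (three indicators for four levels) and clinic site as covariates, keep the arm-by-month terms, and test the month-12 arm effect. State the working association; independence is then acceptable, because the covariate does the adjusting.

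The odds ratio becomes conditional on baseline level. In the simulations the log odds ratio was 0.64 to 0.82, against about 0.60 marginally. So also report standardised 12-month proportions in each level by arm: predict each participant's level probabilities under both arms, then average over the observed baseline levels and sites. This returns to the quantity the plan says it compares.

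The cost is a few sentences of SAP text, a conditional odds ratio to explain and a standardisation step. No new data are needed. If the team prefers to keep the marginal odds ratio, the alternative is to name a non-independence working association and confirm that the chosen software fits it for an ordinal outcome.
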